2. STUDY DESIGN, METHODS, AND PROCEDURES

Study Design

2.1 Study Design: We will conduct a *pilot randomized control trial* of **120** women who deliver at Women and Infant's Hospital of Rhode Island (WIHRI) and plan to receive postpartum care at a WIHRI-affiliated clinic. We will use broad inclusion criteria and analyze data using the intention-to-treat principle to increase generalizability of the findings.

2.2 Eligibility criteria: Inclusion criteria: a) English- or Spanish-speaking b) maternal age ≥ 18 years old, c) smartphone ownership for remote blood pressure ascertainment, d) diagnosis of gestational hypertension, preeclampsia, or chronic hypertension, e) plan to receive postpartum care at a Women & Infants Hospital (WIH)-affiliated clinic. Exclusion criteria: a) fetal anomaly, b) prisoners, c) lack of smartphone, and d) inability to consent.

2.3 Screening, consent, and recruitment: Eligible women will be recruited at the Women and Infant's Hospital of Rhode Island (WIHRI) 's obstetrics units (obstetric triage, labor & delivery, antepartum care unit, and postpartum care unit) during their delivery hospitalization. Recruitment will be conducted by a research assistant or study principal investigator or co-investigator.

2.4 Randomization and blinding: Regardless of when their diagnosis of chronic hypertension, gestational hypertension, or preeclampsia with or without features occurs before or during delivery hospitalization, upon hospital discharge all patients will receive an automatic blood pressure cuff from WIHRI if their insurance does not cover this (or if they do not have one already); for patients whose insurance does cover automatic blood pressure cuffs, the provider will provide them with a prescription for this device at time of diagnosis. This is part of WIHRI's equity initiative related to hypertension: as stated previously, WIHRI has committed to provide non-Bluetooth enabled blood pressure cuffs to all eligible patients.

Those who consent to participate in the study, complete baseline study surveys, and receive a blood pressure cuff prior to discharge will be randomized 1:1 via a computer-generated randomization sequence to one of two protocols: *app based remote blood pressure monitoring* (intervention group) or and standard PNC with SMS-based monitoring (comparison group). The study staff will remain blinded to intervention, except for the research assistant who will be, by necessity, unblinded.

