Since starting recruitment, an additional challenge has developed: up to 10% of participants in the equity program (who may or may not be in the study) are discharged without blood pressure cuffs with the plan for a home visit to provide a BP cuff within 3-7 days after discharge. In addition, about 10% of patients who participated in the study did not complete their baseline study survey. To ensure we obtain a study population of 120 who follow the study protocol, we have developed an alternative approach by changing our inclusion criteria. Specifically, eligible people may be consented and randomized but only those who receive a BP cuff and complete their intake survey prior to discharge will be included in the trial's analytic population. We anticipate needed to randomize up to 160 patients in order to obtain our desired study population of 120 participants.

2.6 Study outcomes and Power:

Primary outcome: The primary outcomes will be adherence to recommended blood pressure check 3-10 days postpartum, as is recommended per standard of care. Our sample size of **120** pregnant women with gestational hypertension or preeclampsia will allow us to detect a 60% increase in adherence to recommended blood pressure check from the baseline rate of 50%, using a two-tailed alpha of 0.05. The 60% improvement (i.e. from 50% to 80% adherence) is conservative as it is less than has been reported in the medical literature.¹⁵⁻¹⁷ **Secondary outcomes:** Secondary outcomes will be surrogate markers of maternal morbidity.

Prespecified secondary outcomes include postpartum readmission for blood pressure management (e.g. hospital admission for blood pressure management within 30 days of discharge), adherence to evidence-based best-practices (e.g. medications, blood pressure ascertainment, postpartum blood pressure goal of $<140/90$), composite severe maternal morbidity (**Table 2**), and composite neonatal morbidity (Table 1). Our study will likely not be powered to detect differences in secondary outcomes due to the rarity of the individual patient outcomes but will provide us crucial pilot data for the subsequent study.

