Provisions to monitor the data to ensure the safety of subjects: Our study does not involve greater than minimal risk. However, we will monitor for unanticipated adverse outcomes. As a part of this, key study personnel (Drs. [name], [name]) will monitor for adverse outcomes on a weekly basis. Should any unanticipated outcomes be found, this will be reported back to the IRB. Beyond the weekly monitoring of patients/data, this will also be performed globally on a quarterly basis.

Withdrawal of subjects: Patients will not be withdrawn from the study.

2.7 Data analysis: Analysis will follow the intention-to-treat principle. Continuous variables will be compared using the Student's *t*-test or Mann Whitney *U* test, as appropriate. Categorical variables will be compared using the χ^2 or Fisher's exact test, as appropriate. We will calculate crude and unadjusted risk ratios and differences. We will use multivariable logistic regression to adjust for potential confounders. Qualitative data obtained from CAHPS survey will also be analyzed using Nvivo, a computer-assisted qualitative data analysis software provided by Brown University. This software promotes inquiry beyond coding, sorting and retrieval of data. It is designed to integrate coding with qualitative linking, shaping, and modeling that may inform health equitable care. [name] and [name] have used Nvivo software. In addition, [name] has utilized this procedure to capture qualitative data previously to successfully design, implement, and launch a new model of health care for vulnerable patients transitioning from the hospital to sub-acute care facilities.²⁷

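### Section 2.5 limits the analysis, after randomisation, to women with a cuff and an intake survey before discharge; this is an unlabelled modified intention-to-treat or per-protocol set and conflicts with the stated intention-to-treat analysis

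*Combined protocol and SAP*

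**What the plan says.** The combined protocol and SAP describes the analysis population in two ways.

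- **Intention-to-treat.** Section 2.1 says the trial will "analyze data using the intention-to-treat principle to increase generalizability of the findings". Section 2.7 repeats it: "Analysis will follow the intention-to-treat principle".
- **Restricted set.** Section 2.5 (potential challenges and alternative approaches) says "eligible people may be consented and randomized but only those who receive a BP cuff and complete their intake survey prior to discharge" will form the analytic population. It adds: "We anticipate needed to randomize up to 160 patients in order to obtain our desired study population of 120 participants". The stated aim is to reach 120 women who keep to the protocol.

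The order of events also differs. Under section 2.4, those who consent, "complete baseline study surveys, and receive a blood pressure cuff prior to discharge will be randomized 1:1". Section 2.5 allows randomisation before either step is done. Section 2.6 (Study outcomes and Power) has surveys collected at randomisation, whereas section 2.5 accepts completion at any time up to discharge.

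Section 2.5 describes the change in these words: "we have developed an alternative approach by changing our inclusion criteria". The criteria in section 2.2 were not altered to match. The inclusion list mentions neither cuff nor survey, and the other list reads in full: "Exclusion criteria: a) fetal anomaly, b) prisoners, c) lack of smartphone, and d) inability to consent".

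Two reasons are given. Up to 10% of women in the hospital's equity programme, who may or may not be trial participants, go home without a cuff. In addition, "about 10% of patients who participated in the study did not complete their baseline study survey".

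**The concern.** Leaving randomised women out because of something that may happen after allocation is not intention-to-treat. The primary comparison therefore has two populations in current text, and the choice between them affects up to a quarter of the women randomised. No analysis of all randomised women is planned, and no count of exclusions by arm.

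Two features make the choice matter.

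1. **Exclusion could depend on arm.** The intervention group receives a Bluetooth cuff, while the hospital programme supplies a routine cuff to all eligible patients. Section 2.5 does not say which cuff counts. If the routine cuff is meant, there is less reason to expect a difference between arms; if the Bluetooth cuff is meant, there is more.
2. **Exclusion could relate to the outcome.** The primary outcome in section 2.6 is adherence to a blood pressure check 3-10 days postpartum. A woman sent home without a cuff is to get one 3-7 days after discharge, and a woman who does not complete a survey may also be less likely to attend a check.

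If both held, the arm that lost more of its less adherent women would look better than it is. Without an all-randomised analysis or by-arm counts, a reader could not tell whether this had happened.

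**Working it through.** The conflict follows from the text and needs no arithmetic. The figures below give its possible size and the cost of resolving it.

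**1. The plan's own sample size.** Inputs from section 2.6: 120 women (60 per arm), 50% versus 80%, two-sided alpha 0.05. No power is stated. Normal approximation: power = Φ[(d − 1.96·SE0)/SE1], with SE0 pooled and SE1 unpooled.

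- SE0 = √(0.65 × 0.35 × 2/60) = 0.0871
- SE1 = √((0.25 + 0.16)/60) = 0.0827
- (0.30 − 1.96 × 0.0871)/0.0827 = 1.56, so power is 94.1% (94.2% by exact enumeration of the z-test)

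**2. How many women could be left out.** Inputs from section 2.5.

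- Ceiling: (160 − 120)/160 = 25%, or 40 women.
- Two losses of 10%, independent: 1 − 0.9 × 0.9 = 19%; 120/0.81 = 148.1, so 149 randomised and 29 excluded.
- Two losses of 10%, no overlap: 20%; 120/0.80 = 150 randomised and 30 excluded.

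The 10% cuff figure is an equity-programme rate, so its use for trial participants is an assumption. The figure of 160 is a ceiling and is not an arithmetic error.

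**3. Illustration of bias. All inputs are assumed:** no true effect, 50% adherence overall in both arms, 10% excluded in one arm and 20% in the other. If excluded women adhere at rate e and a share x is excluded, adherence among those kept is (0.50 − x·e)/(1 − x). Type I error is for the pooled two-sided z-test with 75 or 80 randomised per arm.

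| Excluded (arm A / arm B) | e | Kept, arm A | Kept, arm B | False difference | Type I error |
|---|---|---|---|---|---|
| 10% / 20% | 30% | 52.2% | 55.0% | 2.8 points | 6.2-6.3% |
| 10% / 20% | 40% | 51.1% | 52.5% | 1.4 points | 5.4% |
| 20% / 20% | 30% | 55.0% | 55.0% | 0 | 5.1% |

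In the last row there is no bias between arms, although both arms now describe a more adherent population (55% against 50%).

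Harsher assumptions give more. With 10% versus 25% excluded and e = 0, 0.50/0.75 − 0.50/0.90 = 11.1 points. With 20% versus 30% excluded and e = 25%, 60.7% − 56.2% = 4.5 points.

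**4. Power if all randomised women are analysed.** Control adherence is 50%. Women meeting both conditions reach 80% in the intervention arm. The rest gain nothing (50%) or half the effect (65%).

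| Share not meeting conditions | Their gain | Intervention rate | Per arm | Power |
|---|---|---|---|---|
| 25% | none | 0.75 × 80 + 0.25 × 50 = 72.5% | 80 | 84% |
| 20% | none | 0.80 × 80 + 0.20 × 50 = 74% | 80 | 89% |
| 20% | none | 74% | 75 | 86-87% |
| 25% | half | 0.75 × 80 + 0.25 × 65 = 76.25% | 80 | 94% |
| 20% | half | 0.80 × 80 + 0.20 × 65 = 77% | 75 | 94% |
| 25% | none | 72.5% | 60 | 72% |
| 20% | none | 74% | 60 | 78% |

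**The case against.** The strongest reply is that section 2.5 is an openly stated change, more specific than the general sentences in 2.1 and 2.7. It gives a rule an analyst could apply while comparing women by assigned arm, as many modified intention-to-treat analyses do. Only the label is missing, and this is a pilot meant to give preliminary estimates. Part of this stands: the rule does define a set, and an analyst would not be left without one. The conflict remains, because applying that rule gives an analysis that is not intention-to-treat, and both statements are current text. The pilot is also meant to support an efficacy trial, and section 2.1 justifies intention-to-treat by generalizability.

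A reader might infer more than the documents support:

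- **That section 2.5 reverses the order in 2.4.** It says women may be randomised first, so it permits a different order and does not require it. If the baseline survey is the one section 2.6 schedules at randomisation, that condition may often be met at allocation.
- **That the comparison is biased.** No document gives exclusions by arm or adherence among excluded women. The 1.4-2.8 points are small against the planned 30, and the type I error of 5.4-6.3% should be read against the test's own 5.1%.
- **That late cuffs make women miss the outcome.** One interval runs from discharge and the other from delivery. The time between the two is not given, and nothing says the check must use the home cuff. An overlap is plausible only.
- **That the unblinded research assistant could steer exclusions.** No section says who controls cuff delivery or survey completion.

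It is also fair that the section 2.4 order met practical difficulty, and that receipt of a Bluetooth cuff can only follow allocation.

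**Conclusion.** The point holds as an unreconciled conflict over the primary analysis population. Sections 2.1 and 2.7 state intention-to-treat; section 2.5 restricts the analysis to a subset that may be determined after randomisation, without the label. Sections 2.2 and 2.4 were not brought into line.

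Its size is up to 40 of 160 randomised women (25%), or about 30 if both stated 10% losses apply to trial participants. Differential exclusion is a possibility created by the wording and is not demonstrated. The bias could be nil, 1.4-2.8 points under the main assumed values, or larger under harsher ones, and the documents fix none of these inputs. The case for change rests on the conflict and on the absence of any planned analysis or reporting that would show whether the exclusions were harmless.

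**What to change.** 1. Make the primary analysis all randomised women in their assigned arm, whatever the final number.
2. Keep the cuff-and-survey set as a sensitivity analysis, labelled modified intention-to-treat or per-protocol.
3. State whether the routine or the Bluetooth cuff counts.
4. Report exclusions from the restricted set by arm and reason: no cuff, no survey, both.
5. For women still to be enrolled, reconcile sections 2.2, 2.4 and 2.5 so that the survey is complete and cuff availability is confirmed before randomisation. Availability is the right condition, since receipt of an arm-specific cuff comes after allocation. Few further exclusions should then arise, and the randomised total need not reach 160.

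The choice of primary set should be settled before results by arm are seen.

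**Cost.** Beyond wording, outcomes must be ascertained for the excluded women: about 30 at the stated loss rates and 40 at most. Section 2 says patients will not be withdrawn, which suggests these outcomes can be obtained, but the documents do not confirm that they were collected or say how many women have been randomised or excluded so far. There may be some dilution: power of about 84-89% with 75-80 per arm if 20-25% of women gain nothing, against 94% for 80% versus 50% at 60 per arm. If only 60 per arm are randomised and such women remain among them, it is about 72-78%. If the conditions are confirmed before randomisation and no outcomes are missing, 120 women keep about 94%.

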For this pilot study, sample size limitations will require the use of surrogate markers of maternal morbidity to serve as patient outcomes, which have been selected based on evidence-based best-practices.¹⁻¹⁴ The primary clinical outcome for this study will be blood pressure measurement obtained three to ten days postpartum. Prespecified secondary outcomes include *postpartum readmission for blood pressure management* (e.g. rehospitalizations within 30 days of discharge), *adherence to evidence-based best-practices* (e.g. medications, antepartum surveillance, blood pressure ascertainment, postpartum blood pressure goal of <140/90), *composite severe maternal morbidity* (i.e. stroke, seizure/eclampsia, posterior reversible encephalopathy syndrome, pulmonary edema, heart failure, myocardial infarction, acute fatty liver of pregnancy, hemolysis, elevated liver enzymes and low platelets, placental abruption, post-partum hemorrhage, blood transfusion, acute kidney injury, and transaminitis), *postpartum maternal mortality*, and *composite neonatal morbidity* (i.e. umbilical artery pH <7.10, umbilical artery lactate, seizures, therapeutic hypothermia, hypoxic-ischemic encephalopathy, mechanical ventilation, intrauterine fetal death, neonatal death). We will also explore patient preferences as to treatment group via the Agency for Healthcare Research and Quality Consumer Assessment of Healthcare Providers and Systems (AHRQ CAHPS) survey and compared between both intervention groups and standard prenatal care.²⁵ CAHPS survey will provide mixed quantitative and qualitative assessments. Our *central hypothesis* is that app-based Bluetooth enabled blood pressure monitoring will improve adherence to evidence-based best practices and will demonstrate signals towards improved health equity and maternal morbidity outcomes compared to SMS-based remote blood pressure monitoring.

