They will receive the following per their randomization group:

Standard care (comparison group)

All women will receive education and counseling from their physician providers on evidence-based best-practices and red-flags for pregnancy's complicated by chronic hypertension, preeclampsia, or gestational hypertension. They will participate in WIHRI's ongoing equity initiative using automatic blood pressure cuffs in a remote hypertension monitoring program supported by a nurse practitioner and community health worker.

App-based remote blood pressure monitoring (intervention group)

Women in this group will receive a Bluetooth-enabled automatic blood pressure cuff that sends messages through an affiliated smartphone application to providers upon recording each measurement. This affiliated smartphone application will also contain education on hypertension management. Upon receipt of the blood pressure cuff, participants will be instructed to set up the program/app such that the research assistant (RA) will receive all recorded blood pressure managements. All patients will receive instructions on how to obtain blood pressure and will be instructed to call their on-call provider if the blood pressure is $>160/110$ mmHg. The RA will review each patient's blood pressure log daily to ensure blood pressures remain mild-range (i.e. 140-159/90-109 mmHg) or less.

2.5 Study procedures: Perinatal data will be collected and directly entered by the research assistant or principal investigators into REDCap, a secure database hosted by WIHRI. Data will be collected on a rolling basis to ensure timely collection and monitoring for unseen adverse events.

Potential challenges and alternative approaches: Obtaining our target sample size may be challenging due to the incidence of hypertension diseases of pregnancy in the literature. However, we anticipate having a sufficient population from which to recruit for this pilot study given the 18 month study period and the relatively small sample study. However, should our target sample size be lower than expected, we may expand recruitment into private practice groups who have separate admitting privileges.

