We will also explore patient preferences as to treatment group via the Agency for Healthcare Research and Quality Consumer Assessment of Healthcare Providers and Systems (AHRQ CAHPS) survey and compared between both intervention groups and standard prenatal care.²⁵ Per AHRQ guidelines, 100 CAHPS surveys must be completed in a pilot study to determine a difference in patient experience between care models.²⁵ Our study population of **60 women** per group (120 women total) is anticipated to generate ~100 completed surveys per group (200 total), based on an anticipated response rate of 80% and each participant completing two surveys. Upon enrollment, participants will choose whether they desire to complete the AHRQ CAHPS surveys in paper, online through email, or via a text-message platform; regardless of route, surveys will be collected at randomization and at ~30-45 days postpartum.

On the second survey, participants will also complete a validated scale, the Decision Regret Scale.²⁶ Of note, both the AHRQ CAHPS study and the Decision Regret Study are already validated in Spanish.

2.6 Data Management, Sources of Materials, Records/Data to be reviewed: Antepartum, maternal/neonatal, pregnancy, and perinatal data will be collected and directly entered by the research assistant or principal investigator into REDCap, a secure database hosted by WIHRI. All primary and secondary outcomes will be entered into REDCap by the RA or study team. Thus, the data to be reviewed will only be collected by key study personnel. In addition, pregnancy characteristics (maternal weight, disease comorbidities, etc.) and demographic information (reported race/ethnicity, insurance type, zip code) will be collected post-delivery and entered into REDCap. Prior to data analysis, all patient identifiable information will be stripped to ensure patient confidentiality. Our REDCap database will be encrypted by multiple levels of password protection (accessing computer, network, and logging into database) that will only be accessible by key research personnel. Anti-virus software is installed and up to date and the operating system is up to date with all Windows and Apple updates.

Material/Specimen Management: No specimens will be stored outside of standard care (such as umbilical cord gases processed by laboratory per usual clinical protocol).

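### The ~100 CAHPS surveys per group include those taken at randomization; only about 48 per group can measure experience of the assigned monitoring

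*Combined protocol and SAP*

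**What the plan says.** Section 2.6 (Study outcomes and Power) sets a benchmark for the CAHPS survey: "100 CAHPS surveys must be completed in a pilot study to determine a difference in patient experience between care models". It answers that benchmark with 60 women per group, "anticipated to generate ~100 completed surveys per group (200 total), based on an anticipated response rate of 80% and each participant completing two surveys". On timing it says that "surveys will be collected at randomization and at ~30-45 days postpartum". The results are to be "compared between both intervention groups and standard prenatal care". Section 1 adds that the "CAHPS survey will provide mixed quantitative and qualitative assessments".

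Three other places bear on when the first survey is answered:

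- Section 2.4 describes women who "complete baseline study surveys, and receive a blood pressure cuff prior to discharge will be randomized 1:1", so the baseline survey comes before allocation.
- Section 2.5, describing a change made after recruitment began, says "eligible people may be consented and randomized but only those who receive a BP cuff and complete their intake survey prior to discharge" enter the analysed population. The intake survey can then follow randomization.
- Section 2.4, for the intervention group, says: "Upon receipt of the blood pressure cuff, participants will be instructed to set up the program/app".

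Section 2.7 gives general two-group tests, and logistic regression to adjust for confounders. For CAHPS it specifies only the qualitative analysis. It names no change score, baseline adjustment or repeated-measures model for the quantitative scores.

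**The concern.** The benchmark concerns a difference between care models, but half the surveys offered to meet it are taken at randomization, during the delivery hospitalization. A woman answering then has little or no experience of the remote monitoring she will use after discharge. Her answers cannot measure an effect of it. Two surveys from one woman are also not two independent observations.

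A reader who takes about 100 per group at face value would credit the quantitative patient-experience result with roughly twice the information it has. Acceptability is one of the pilot's stated aims, and the pilot is meant to support a later efficacy trial. The plan also does not rule out pooling both surveys in one two-group test. That would dilute any arm difference and ignore the correlation within women.

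**Working it through.** **Inputs from section 2.6 (Study outcomes and Power).** 60 women per group, 120 in total; 80% response; two surveys per woman, one at randomization and one at about 30-45 days postpartum; benchmark of 100 completed surveys.

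**The plan's own figure.** 60 × 2 × 0.80 = 96 per group, and 2 × 96 = 192 in total. The plan rounds these to ~100 and 200.

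**Surveys that can show an arm difference.** Only the second survey counts, so the number is 60 × response rate:

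| Response at 30-45 days | Per group | Total |
|---|---|---|
| 70% | 42 | 84 |
| 80% (as planned) | 48 | 96 |
| 90% | 54 | 108 |
| 100% | 60 | 120 |

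**Against the benchmark.**

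- Per group: 48 of 100, with a ceiling of 60. Reaching 100 at 80% response would take 100/0.80 = 125 women per group.
- Study total: 96 of 100, which is 4% short. A response of 100/120 = 83.3% would reach it.

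**Precision.** The plan gives no alpha, power, SD or effect size for CAHPS. I assume a continuous score, two-sided 5% alpha and 80% power. The detectable difference in SD units is (1.960 + 0.842) × √(2/n):

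- n = 48: 0.57 (n = 42: 0.61; n = 54: 0.54)
- n = 100 independent responses: 0.40

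**What the first survey can restore as a covariate.** With r the correlation between a woman's two scores (assumed 0.3 to 0.7; the plan gives none):

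| Scenario | Multiplier or n | r = 0.3 | r = 0.5 | r = 0.7 |
|---|---|---|---|---|
| All 48 have a usable baseline | 0.572 × √(1 − r²) | 0.55 | 0.50 | 0.41 |
| All 48 kept, 80% with a usable baseline, overall mean for the rest | 0.572 × √(1 − 0.8r²) | 0.55 | 0.51 | 0.45 |
| Only women with both surveys, responses independent | n = 60 × 0.80 × 0.80 = 38.4, times √(1 − r²) | 0.61 | 0.55 | 0.46 |

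In the first row the adjusted analysis is worth 48/(1 − r²) unadjusted women per group: 53, 64 and 94. In the last row, at r = 0.3, dropping women without a baseline (0.61) does worse than no adjustment (0.57).

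The last two rows apply only if some first scores are missing or were given after allocation was known. If the intake survey contains the CAHPS and always precedes allocation, every analysed woman has a usable baseline and the first row applies.

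**The case against.** The strongest reply is that nothing is miscalculated or hidden. The plan shows every factor and both survey times, forecasts completed surveys, and claims no power for CAHPS. Its benchmark sentence names no group, so it reads naturally as a study total, and on that reading follow-up alone comes within 4%. If the intake survey includes the CAHPS, all 60 analysed women per group have a first score, and the survey count is 60 + 48 = 108, so about 100 is not inflated as a count. If standard prenatal care is a separate comparator, the surveys at randomization are relevant to that comparison. An unadjusted test at 30-45 days is already permitted. At r = 0.7 the adjusted analysis is worth about 94 women per group. And CAHPS is exploratory.

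Much of this stands. The fault lies in what is counted, not in the multiplication. The shortfall against the benchmark is serious only on the per-group reading. The SD figures rest on my assumptions, and the 38-per-group case is conditional. Baseline adjustment is a recommendation, since the unadjusted test is valid.

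What does not stand is using the two-survey count to support a between-arm difference. The gain at r = 0.7 needs a high correlation, a first survey answered before allocation, and an analysis the plan does not specify. The comparison with standard prenatal care is also unclear: section 2.4 describes the control arm itself as standard prenatal care with SMS monitoring, so it may not be a separate comparator.

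**Conclusion.** The concern holds. The stated yield is about twice the number of surveys that can measure an arm difference: about 48 per group (96 in total) at 80% response, and 42 to 54 per group at 70% to 90%. The count assumes 60 analysed women per group and that the 80% applies to the 30-45 day survey, for which the plan gives no separate rate.

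The size of the shortfall is open until the plan says what the 100 refers to. Two further points need settling: whether the intake survey contains the CAHPS, and whether it is always answered before allocation is known, since sections 2.4 and 2.5 differ on this. The effect is confined to the quantitative part of an exploratory outcome. It is worth correcting because the plan offers the figure as its only numerical support for that comparison.

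**What to change.** In section 2.6 (Study outcomes and Power):

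- Restate the yield as about 48 follow-up CAHPS surveys per group (96 in total) at 80% response, plus those collected at randomization. Drop the claim of about 100 per group for the between-arm comparison.
- Say whether the 100 is per group or overall, and whether the intake survey includes the CAHPS.
- If the surveys at randomization are to serve a comparison with standard prenatal care, say so and define that comparator.

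In section 2.7, add wording such as:

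> The between-arm CAHPS comparison uses the 30-45 day score, one record per woman, adjusted for her score at randomization where that survey was completed before allocation was known. Women in the analytic population without such a score are kept, with the overall baseline mean in its place.

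This keeps every analysed woman who answers at follow-up. It does not by itself change the rule in section 2.5 on who enters the analytic population. An unadjusted test of the 30-45 day score would also be valid, though usually less precise.

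The cost is some rewording, one analysis rule, and a record of whether each first survey preceded knowledge of allocation. No extra women, visits or surveys are needed. The drawback is a less favourable stated yield.
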